### **11.1.3. Prior and Concomitant Therapy**

A concomitant therapy is any drug or substance administered from 30 days prior to the Screening Visit through the Final Safety Follow-Up Visit. Bypassing agents used during the study are considered concomitant therapy and should be recorded as such. For subjects who are receiving breast milk, any drug or substance being administered to the mother during the period when she is breastfeeding will also be considered a concomitant medication. Maternal concomitant medications will also be collected, unless the breast milk is derived from a source other than the mother. Maternal concomitant medications will no longer be collected after the discontinuation of breastfeeding.

The subjects or caregivers will be instructed that the subject should not start any new medications, including nonprescription drugs and herbal preparations, unless they have received permission from the Investigator.

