### **13.1.4.2. Data to Be Captured**

It is required that the subject/caregiver enter dosing information on rFVIIIFc and/or FVIII bypassing agents into the EPD immediately after an injection or within a maximum of 7 days, to ensure data integrity and to facilitate appropriate medical review and dosing guidance.

In the event of a bleeding episode, the following information will be collected in the EPD or eCRF and medical records:

- The type of bleeding episode (i.e., spontaneous or traumatic) and if related to sports activity or physical activity
- The date the bleeding episode occurred
- The product (rFVIIa, aPCCs, FVIII product [include specific drug name], etc.) and dose administered to treat the bleeding episode including any repeat doses
- The location of the bleeding episode

The EPD will serve as the source document for bleeding episodes between visits. Bleeding episodes during clinical visits will be recorded in the eCRF.

The clinical sites and Clinical Monitors will ensure that there is consistency between the subject's medical record, dispensing records, source documents, EPD, and eCRFs. During the clinic visits, the Investigator will verify whether a bleeding episode has occurred and was "spontaneous" or "traumatic." The subject or caregiver will also be reminded about timely EPD completion.

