1.1 STUDY DESIGN

This is an open-label, single-arm, interventional, multicenter study designed to explore the use of rFVIIIFc (recombinant coagulation factor VIII Fc fusion protein)([1](#))[\(2\)](#) for ITI (Immune Tolerance Induction). The study will be conducted in male patients of any age with severe hemophilia A and high-titer inhibitors (historical peak ≥ 5 BU/mL), who have been previously treated with any plasma-derived FVIII or recombinant conventional or EHL (extended half-life) FVIII and are undergoing ITI treatment for the first time.

The study period consists of 1) a 4-week (1-month) Screening Period; 2) a maximum of a 48-week (12-month) ITI Period; 3) a minimum of a 16-week (4-month) Tapering Period after all criteria for tolerization have been met; and 4) a 32-week (8-month) Follow-Up Period. Only patients who achieve ITI success will enter the Tapering and Follow-Up Periods. During the Tapering and Follow-Up Periods, the patient's dose will be adjusted to achieve the prophylactic dose. However, if FVIII peak activity levels rise above 200 IU/dL after the inhibitors are negative but before all the ITI success criteria are met, the dose may be adjusted according to Investigator judgment to maintain the FVIII peak activity levels between 100 and 200 IU/dL. This dose reduction will not be considered part of the Tapering Period, and the patient will maintain the schedule of assessments per the ITI Period.

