Adherence to the treatment regimen at each period is defined in 2 ways. Dose adherence is defined as the percentage of administered doses as registered in the EPD and EDC versus the prescribed doses to a patient. Dosing frequency adherence is defined as the percentage of number of days with infusions as registered in the EPD and EDC compared to the prescribed number of days to a patient in that period.

Consumption during ITI

Consumption of rFVIIIFc at each period is defined as the total rFVIIIFc in IU/kg which is received by a patient in that period.

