Patients' first and last doses and dosing frequencies during the tapering period, and the last prophylactic doses and dosing frequencies during the follow-up period will be summarized using TPFAS and FUPFAS, respectively.

Consumption

Total consumption of rFVIIIFc during the study (excluding use of study drug for the purpose of surgery, and for the assessment of IR and $t_{1/2}$) will be summarized descriptively using the ITIFAS. Analysis will also be conducted separately for each of the 3 treatment periods using their respective analysis set. Summary statistics of annualized total consumption will also be provided.

The rate for each patient will be annualized in order to account for difference in the duration of ITI treatment based on the equation below:

$$\text{Annualized total consumption} = \text{total consumption} * \frac{365.25}{\text{length in study (days)}}$$

Patients will be included in this analysis only if they were observed for at least 90 days.

Adherence

Overall adherence to dosing regimen of rFVIIIFc (excluding use for the purpose of surgery and for the assessment of IR and $t_{1/2}$) will be calculated in two ways as follows:

$$\text{Dose adherence (\%)} = \frac{\text{total dose administered as registered in diary and EDC}}{\text{total dose prescribed}}$$

$$\text{Frequency adherence (\%)} = \frac{\text{total number of days with infusions as registered in the diary and EDC}}{\text{total number of days on which infusion was prescribed}}$$

This calculation will be done for each study period, and the results will be listed and summarized descriptively using the respective analysis sets.

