The prior and concomitant and post-treatment medications will be summarized for the ITIFAS population. Summaries will be based on the number and percentage of patients taking medications by WHODRUG standardized medication text. Within each WHODRUG standardized medication text a patient will be counted once even if he reported taking the medication more than once. Separate summaries will be provided for prior and concomitant medications. Medications taken after the EOS visit up to the Follow-Up visit/phone call will not be included in the summary table of concomitant medications. Two listings will be provided, one for prior and concomitant medications taken through the EOS visit and the other for the post-treatment medications taken after the EOS visit and prior to the Follow-Up visit/phone call. The summaries will be sorted in alphabetical order.

In this study, for patients who receive breast milk, maternal concomitant medications are also be collected at the same time points as other concomitant therapies, unless the breast milk is derived from a source other than the mother or the mother did not consent. These will be presented in a similar way as other concomitant medications.

Bypassing agents

Number and percentage of patients who used bypassing agents (aPCC [FEIBA] or rFVIIa [NovoSeven]) prior to first dose of ITI with rFVIIIFc and during each of the study periods will be tabulated by type of bypassing agents and regimen (on-demand versus prophylaxis). Total consumption of bypassing agents will be tabulated by type of bypassing agents and by study period as well as combined. Information from different data sources, e.g., concomitant medications, ePD and in-clinic use, will be integrated for this analysis.

Other therapies and procedures

Other therapies administered and concomitant procedures performed within 30 days prior to the first dose of study drug through the end of the study will be listed only, a summary table is not planned.

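### Bypassing-agent consumption is tabulated only as totals by study period, with no stated unit, per-kg scaling or time denominator, so amounts cannot be compared between periods

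*SAP*

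**What the plan says.** SAP 5.2, under the bypassing-agents paragraph, plans two summaries. The first is a count of users: "Number and percentage of patients who used bypassing agents (aPCC [FEIBA] or rFVIIa [NovoSeven]) prior to first dose of ITI with rFVIIIFc", and the same during each study period, by agent and by regimen (on-demand or prophylaxis). The second is the amount used: "Total consumption of bypassing agents will be tabulated by type of bypassing agents and by study period as well as combined". The paragraph gives no unit for either agent, no per-kg or per-patient statistic, no time denominator, no minimum observation time and no analysis set. It also does not say whether the combined figure is across periods or across agents. Concomitant-medication, diary and in-clinic records are to be integrated, without a stated rule for doing so.

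The same SAP treats the study drug differently. In 4.4.1.1, "Consumption of rFVIIIFc at each period is defined as the total rFVIIIFc in IU/kg which is received by a patient in that period". In 4.7.1 an annualized version is added for patients observed for at least 90 days, with the reason given: "The rate for each patient will be annualized in order to account for difference in the duration of ITI treatment".

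SAP 1.1 sets the period lengths: "a maximum of a 48-week (12-month) ITI Period", "a minimum of a 16-week (4-month) Tapering Period after all criteria for tolerization have been met", and 32 weeks of Follow-Up. Only patients with ITI success enter the last two periods, and males of any age may enrol.

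**The concern.** A total over a period is the product of how much is used per patient-week per kg, how many patient-weeks were observed, and how heavy the patients are. Only the first factor describes bypassing-agent use. The other two change between periods by design: ITI may last up to three times the minimum Tapering Period, and non-responders contribute to ITI only. Body size enters through the mix of patients who continue. It also separates one patient from another within a period.

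Protocol 7.2.2.1 links stopping bypassing agents to a negative titer or to sufficient hemostatic control with rFVIIIFc, so a reader will naturally take a lower total after ITI as a sign of benefit. Part of any such fall may be real and part may be lost patient-time, and the planned table gives no means of telling them apart. The reason the SAP gives for annualizing rFVIIIFc consumption applies equally here.

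**Working it through.** The documents give no consumption figure, so there is nothing to reproduce. The check asks what the ratio of period totals would be if true use per kg per patient-week were the same in every period, with equal body weights. That ratio then equals the ratio of patient-weeks.

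**Inputs**
- N = 17 (Protocol 16.1). SAP 2 says up to 30, so both were run.
- Success proportion 33% to 88%: the range of published rates in Protocol 5.1, used here as an assumption.
- Time to success, t, from 17 to 48 weeks: 17 is the shortest rFVIIIFc case in Protocol 5.2.3 and 48 is the maximum. This is also an assumption.
- Tapering 16 weeks, Follow-Up 32 weeks, non-successes on ITI for 48 weeks, no withdrawals or relapses.

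**Formulas**, with s = N × success proportion, rounded:
- ITI = s·t + (N − s)·48
- Tapering = s·16
- Follow-Up = s·32

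**Results for N = 17, in patient-weeks**

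| Success | s | t | ITI | Tapering | Follow-Up | ITI:Tapering | ITI:Follow-Up |
|---|---|---|---|---|---|---|---|
| 33% | 6 | 17 | 6·17 + 11·48 = 630 | 96 | 192 | 6.56 | 3.28 |
| 33% | 6 | 48 | 17·48 = 816 | 96 | 192 | 8.50 | 4.25 |
| 88% | 15 | 17 | 15·17 + 2·48 = 351 | 240 | 480 | 1.46 | 0.73 |
| 88% | 15 | 48 | 17·48 = 816 | 240 | 480 | 3.40 | 1.70 |

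Follow-Up:Tapering is 32/16 = 2.00 in every row. For N = 30 the ITI:Tapering ratio runs from 634/416 = 1.52 to 1440/160 = 9.00. The SAP allows failure to be declared at Week 36. If every non-success left then, the lowest ITI:Tapering ratio would be (15·17 + 2·36)/240 = 327/240 = 1.36, so the conclusion is unchanged.

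**Body size.** At equal per-kg use, a 70 kg patient adds 70/10 = 7 times the amount of a 10 kg patient, and a 20 kg patient adds 2 times. These weights are assumptions, since the documents give no weight distribution.

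**How much of an observed ratio is patient-time?** Let T be the patient-time ratio and RR the true ITI:Tapering rate ratio. The observed ratio of totals is RR·T, and the share of its logarithm due to patient-time is log(T)/log(RR·T).

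| RR | T = 1.46 | T = 8.5 |
|---|---|---|
| 1 | 100% | 100% |
| 2 | 35% | 76% |
| 5 | 19% | 57% |
| 20 | 11% | 42% |

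Patient-time is a material part of the ratio over much of this grid. Whether it is the larger part depends on RR, which is unknown.

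**The case against.** The best defence is that the SAP leaves the measure undefined rather than choosing unadjusted totals. In 4.7.1 it uses the same term, total consumption, for a quantity that 4.4.1.1 defines in IU/kg, and a programmer might carry that over. This stands in part: nothing in 5.2 rules out a per-kg figure. But the definition is confined to rFVIIIFc, and a time denominator cannot be read into the bypassing-agent sentence.

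The table is also descriptive. No test or planned contrast uses it, bleeding rates are annualized separately, and the number and percentage of users by period is planned alongside. Bypassing-agent consumption is not among the visible endpoints. SAP 4.5 is not visible in the public copy, so a fuller definition there cannot be excluded. All of this stands, and it limits the importance of the point.

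A reader might infer more than the documents support:
- *That the totals mostly reflect period length and attrition.* This is not shown. Protocol 7.2.2.1 and 7.2.4 lead one to expect a real fall once the titer is negative, and with a 20-fold fall patient-time accounts for 11% to 42% of the log ratio.
- *That the totals must fall after ITI.* They need not. With 88% success at 17 weeks, Follow-Up has 480 patient-weeks against 351 in ITI.
- *That one adult would dominate.* With sixteen children of 12 kg and one adult of 70 kg (assumed), the adult contributes 70/(16·12 + 70) = 27%, a large share but not a dominant one.
- *That home doses will be counted twice.* The protocol does ask for two records: "Bypassing agents used during the study are considered concomitant therapy and should be recorded as such" (11.1.3) and "It is required that the subject/caregiver enter dosing information on rFVIIIFc and/or FVIII bypassing agents into the EPD" (13.1.4.2). But the SAP says sources are integrated, not stacked, and 13.1.4.2 requires sites and monitors to keep them consistent.
- *That the wrong denominator will be used.* SAP Table 2 assigns an analysis set to each period. The paragraph does not name one, which is a missing detail and not an error.

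**Conclusion.** The point holds as a low-severity improvement. The only planned measure of the amount of bypassing agent used is a by-period total with no unit, weight scaling or time denominator, while the SAP applies both adjustments to rFVIIIFc. Under equal true use, patient-time alone moves the ITI total to between 1.46 and 8.50 times the Tapering total, and between 0.73 and 4.25 times the Follow-Up total, so even the direction of the second comparison is not protected. Body size adds a further multiplier between patients. The figures rest on N = 17, the assumed ranges for success and time to success, nominal period lengths and no dropout; a longer Tapering Period would lower the first ratio. They show that the totals cannot distinguish a real fall from lost patient-time. They do not show that a real fall is absent or small.

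**What to change.** In SAP 5.2, keep the totals, state the unit for each agent, say what is combined, and add the following separately for aPCC and rFVIIa:

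- Per-patient amount per kg in each period, using the most recent weight before the dose, as 4.7.1 does for rFVIIIFc.
- The same figure annualized by that patient's days in the period (the 4.7.1 formula divides by length in study), restricted to patients observed for at least 90 days, as the SAP already requires for rFVIIIFc.
- A pooled rate for each period: total amount per kg divided by total patient-time, including all patients, so that those under 90 days are not lost.
- The number of patients and patient-time beside every by-period figure, on the ITIFAS, TPFAS and FUPFAS respectively.

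Also add one sentence on integrating the sources: match records on product, date, dose and, where recorded, time. Matching on date alone could delete genuine additional doses given the same day.

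The cost is SAP wording and minor programming. The protocol already collects weights, bypassing-agent doses and visit dates. The drawback is that individual annualized rates will be unstable with few users, which is why the pooled rate should stand beside them.

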5.3 APPENDIX 3 DATA HANDLING CONVENTIONS

Description of study days

Study day for an event will be calculated from the first dose of study drug as (date of event – first dose date + 1) if the date of event is on or after the first dose date, or (date of event – first dose

date) if the date of event is before the first dose date. That is, Study Day 1 is the first day of treatment with study drug rFVIIIFc. Study Day -1 is the day immediately preceding Study Day 1. There is no Study Day 0 in this study. Study days will be included in the data listings where indicated on the listing shells. "NA" for "not applicable" will be used to indicate that a patient did not receive the respective study drug.

Analysis windows for time points

Not applicable

Missing data

Aside from the following, no rFVIIIFculation of study data will be performed.

For the analysis of AEs and concomitant medications/procedures, if the stop/start date of an AE or a concomitant medication is missing or partial, the corresponding study day will be left blank. However, inferences will be made from the partial and missing dates to classify medications as prior and/or concomitant and AEs as treatment emergent (or not).

For an AE with a partially or completely missing onset date, the following algorithm is used:

- If the onset time of an adverse event (if time is collected) is missing and the date of onset is the date of dosing, the AE is considered a TEAE.
- If the onset day of an adverse event is missing and the month and year of the onset of the AE are either the same or later than the month and year of the first treatment, the AE will be considered a TEAE.
- If the onset day of an adverse event is missing and the month and year of the onset of the AE precede the month and year of the first treatment, the AE will not be considered a TEAE.
- If the onset month of an adverse event is missing and the year of the onset of the AE is either the same as or later than the year of first treatment, then the AE will be considered a TEAE.
- If the onset month of an adverse event is missing and the year of AE onset precedes the year of first treatment, the AE will not be considered a TEAE.
- If the onset day, month, and year of an adverse event are missing, the AE will be considered a TEAE.
- If start date is partial but the stop date can be determined to be before the start of the first dose of study drug, then the AE will not be considered a TEAE.

For concomitant medications with partial dates, if a concomitant medication start day is missing, the medication will be classified as both a prior and a concomitant medication unless the start month and/or year or the medication stop date can be used to determine whether a medication is concomitant or prior using the following algorithm:

- If a concomitant medication has a missing start day, but the month and year are before the start month and year of the first dose of rFVIIIFc and the stop date of the medication is

before the start day of the first dose of rFVIIIFc, the medication will be classified as prior only.

- If the day of the medication start date is missing and the month and year are after the month and year of the first dose of rFVIIIFc, the medication will be classified as concomitant only.
- If the month of the medication start date is missing and the year is before the start year of the first dose of rFVIIIFc and the stop date of the medication is before the start date of the first dose of rFVIIIFc, the medication will be classified as prior only.

